### **Debriefing Procedures.**

In this study, it is necessary for the patients to be blinded to their treatment arm (placebo vs. Exparel®). Withholding this information is necessary in order minimize bias and control for a possible placebo effect. Following completion of the study, the subjects will be debriefed at their follow-up appointment, approximately 30 days following their surgery. During this debriefing, the patient's study arm will not be

revealed. If the patient wishes to know their study group assignment, then they may be informed of their group assignment following completion of the entire study. They will have the opportunity to ask any questions and express any concerns regarding study participation.

**Documentation of Consent:** Signed consent forms will be stored in the locked office of the co-PI, [name].

**Costs to the Subject:** There is no additional cost to the subjects for participating in this study.

**Payment for Participation:** There are no incentives (monetary or otherwise) for participation in this research study.

**Appendix I: Study schedule and procedures**

**Table 2: Study schedule and procedures**

Procedure	After Study Drug Administration														
	2-72 Hours														Site Visit
	Time post-drug				0	2	4	8	12	24	36	48	60	72	
	Study Day	Day -30 to -1	Day -1 to 1	1	1	1	1	1	1	2	2	3	3	4	30
Time Window (±h)					0.25	0.25	0.5	0.5	1	2	2	4	4	96	
Informed consent	X														
Drug screen	X														
Clinical labs 	X														
Assess/confirm eligibility	X	X													
Medical history, demographics and baseline characteristics	X	X													
Train self-assessments	X	X													
Pregnancy test (women of childbearing potential)		X													
Physical examination	X	X													
Randomize subject & prepare study drug		X													
Vital signs 	X	X			continuous monitoring in CVICU				X	X	X	X	X	X	X
ECG	X				Continuous monitoring										
Neurological assessment	X				X	X	X	X	X	X	X	X			
Inspiratory capacity		X 								X 	X 	X 			
Study drug administration				X											
NVPS rating 					1h	X	X	X 	X 						
NRS rating 		X						X 	X 	X	X	X	X	X	
PCA								X	X	X	X	X			

**Table 2: Study Schedule and Procedures (Cont.)**

Procedure	After Study Drug Administration														
	2-72 Hours														Site Visit
	Time post-drug				0	2	4	8	12	24	36	48	60	72	
	Study Day	Day -30 to -1	Day -1 to 1	1	1	1	1	1	1	2	2	3	3	4	30
	Time Window (±h)					0.25	0.25	0.5	0.5	1	2	2	4	4	96
Oral narcotics												X	X		
Subject's satisfaction with postoperative analgesia									X				X	X	
Brief Pain Inventory	X													X	
Record occurrence and duration of nausea/vomiting					X	X	X	X	X	X	X	X	X	X	
Record date/time of each bowel movement					X	X	X	X	X	X	X	X	X	X	
Record date/time of each rescue pain medication dose					X	X	X	X	X	X	X	X	X	X	
Subject productivity (date subject returned to work or normal daily activities)														X	
Concomitant medications 	X	X	X	X	X	X	X	X	X	X	X	X	X	X	
Record AEs and SAEs					X	X	X	X	X	X	X	X	X	X	

 Clinical labs will include Complete Metabolic Panel, CBC and INR/PTT.

 Temperature, heart rate, blood pressure, oxygen saturation will be monitored continuously in the cardiovascular ICU (CVICU) and at the time points listed.

 Inspiratory capacity (IC) will be measured using the handheld spirometer at baseline (pre-op) and then once between POD #1-2.

 Pain will be assessed with the NVPS or NRS scores at the end of anesthetic and before the first dose of rescue pain medication.

 Pain will be assessed with NVPS if the patient is still intubated and/or sedated. Pain will be assessed with the NRS score if the patient is extubated and alert/responsive.

 All medications that the subject used within 3 days prior to surgery will be recorded; including medication name, dose and date last taken.

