### Patient enrollment

Screening procedures will be performed in the outpatient clinic, inpatient floor or cardiac cath lab. During the screening visit, medical/surgical history, vital sign measurements, and routine clinical laboratory tests, which are normally obtained in all cardiac surgery patients (complete metabolic panel, CBC, INR/PTT). If the patient meets eligibility criteria and is willing to participate, then informed consent will be obtained. Consenting patients will also undergo drug/alcohol screening and forced vital capacity (FVC) measurement prior to surgery. The patients will be trained on the pain assessment tools used during the study, including the adult NVPS and NRS (see Appendix II).

Prior to the planned operation, patients will be administered the Brief Pain Inventory to establish baseline pain scores (see Appendix III). The patient will also receive a sheet reviewing the NVPS and NRS pain assessment scales and be asked to rate their pain on the NRS scale. They will also be instructed on how to use the PCA pump prior to surgery.

On the day of surgery, the subjects' history, physical and labs will be reviewed by research staff to confirm study eligibility. They will also be instructed on how to use the incentive spirometer and their peak inspiratory capacity (IC) will be measured.

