### Randomization and Blinding

Patients will be randomized on the day of surgery to either placebo or treatment group. The subjects will be randomized in blocks of 4 to ensure a 1:1 ratio of placebo to treatment groups.

- Placebo: 0.9% normal saline
- Treatment group: 0.53% Exparel®

A randomization sheet will be generated by the study pharmacist, listing the randomization schedule in sequence for each block. The study pharmacist will have control of the randomization sheet. At the time of randomization, he will go to the next available row to determine which medication to dispense. The randomization sheet will document each subject's number, initials, date of surgery and study arm (active or placebo).

The study pharmacist will hold the key identifying which study group corresponds with which letter. In order to maintain blinding of the study investigators, the pharmacist will not reveal the subject's group assignment and data collection will be done according to the subject number. At quarterly intervals during the trial, the study pharmacist will reveal the blinding to the Independent Data/Safety Monitor (DSM) only. This will enable the Independent DSM to capture for any alarming trends in adverse events or serious adverse events as they are occurring. At completion of data collection and analysis for the entire study, the pharmacist will provide the study investigators with a copy of the report revealing which subject belonged to which study group.

The subjects will be blinded to their study arm and remain blinded for the entire duration of this study. Subjects who wish to know which drug they received (Exparel® or placebo), may contact the PI or co-PI and they will be informed of their study group following completion the study.

The study investigators, surgeon administering the medications, operating room staff and ICU/floor staff will all remain blinded. Only the pharmacist who will prepare and dispense the medication will be unblinded.

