#### Other variables:

Splinting can occur from inadequately controlled pain, resulting in the subject avoiding deep inspiration. The degree of splinting will be measured by a change in bedside inspiratory capacity (IC) at post-operative day 1-2 from preoperative IC.

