### **Data Analysis.**

#### Data Analysis

- Patient demographics/Pre-op characteristics:
  - Age, sex, race, Body surface area (BSA)/BMI
  - Co-morbid diseases: Diabetes mellitus, COPD, smoking, hypertension, coronary artery disease
  - Left ventricular ejection fraction (%)

- Creatinine (Cr), Cr clearance
- Functional status: New York Heart Association (NYHA) class, American Society of Anesthesiologists (ASA) classification
- Intra-operative characteristics:
  - Operation type: CABG (on/off bypass), AVR, MV repair/replacement, Maze, Other (i.e. TV repair/replacement, ASD closure)
  - Internal mammary artery (IMA) harvested (one or two)
  - Cardiopulmonary bypass time (min)
  - Aortic cross-clamp time (min)
  - Intraoperative fentanyl ( $\mu\text{g}$ ), intraoperative versed (mg)
- Pain assessment:
  - Calculate mean area under the curve (AUC) for adult NVPS scores over the time intervals “0-2”, “0-4”, “0-8” and “0-12” hours.
  - Calculate mean AUC for NRS scores over the time intervals “0-12”, “0-24”, “0-36”, “0-48”, “0-60” and “0-72” hours.
- Opioid requirement:
  - Calculate mean cumulative fentanyl equivalent use for time intervals “0-2”, “0-4”, “0-8”, “0-12”, “0-24”, “0-36”, “0-48”, “0-60” and “0-72” hours.
  - Use of breakthrough pain medication (e.g. Toradol or Tramadol)
- ICU length of stay:
  - Calculate mean lengths of stay (hours) for placebo and Exparel® groups.
- Hospital length of stay:
  - Calculate mean lengths of stay (days) for placebo and Exparel® groups.
- Time to extubation:
  - Calculate mean time to extubation (hours) for placebo and Exparel® groups.
- Time to return of bowel function:
  - Calculate mean time to return of bowel function for placebo and Exparel® groups.
- Splinting
  - Mean change in IC from pre-operative to POD #1-2 in both treatment arms.
- Assessment of blind
  - Calculate the percentage of correctly guessed treatment assignments.

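### Inspiratory capacity is read once after surgery in an unspecified slot (24, 36 or 48 h) and analysed as raw change without regard to timing, which adds avoidable noise

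*Combined protocol and SAP*

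**What the plan says.** Methods, Other variables, defines the degree of splinting as the "change in bedside inspiratory capacity (IC) at post-operative day 1-2 from preoperative IC". The baseline value is taken on the day of surgery, when patients are taught the incentive spirometer and "their peak inspiratory capacity (IC) will be measured" (Patient enrollment). For the post-operative value, footnote 3 to Table 2 (Appendix I) says: "Inspiratory capacity (IC) will be measured using the handheld spirometer at baseline (pre-op) and then once between POD #1-2".

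The "Inspiratory capacity" row of Table 2 has one pre-operative mark and three post-operative marks, all carrying footnote 3. By column count the three fall at 24, 36 and 48 h, with windows of ±1, ±2 and ±2 h. The neurological row supports this alignment: its eight post-dose marks match the times listed under Cardiac and Neurologic Monitoring, which end at 48 h.

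The Data Analysis list gives one item for splinting: "Mean change in IC from pre-operative to POD #1-2 in both treatment arms". Statistical analysis provides t-tests or rank sum tests for continuous outcomes and names regression for NRS scores and opioid requirements. It mentions no model for IC.

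A second lung measurement appears once, under Patient enrollment: "Consenting patients will also undergo drug/alcohol screening and forced vital capacity (FVC) measurement prior to surgery". It has no row in Table 2, no follow-up value and no place in the analysis list.

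**The concern.** Each patient contributes one post-operative IC value, and the plan does not say which of three slots it comes from. The footnote asks for one reading, the table offers three times, and POD is not defined in hours. IC may well change over the day between the first and last slots as pain, opioid use and effort change. Two patients with the same recovery could then show different changes from baseline only because they were tested at different hours.

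The plan does not ask for the hour of the IC test, although Table 2 does ask for the date and time of bowel movements and rescue doses. If the hour is not kept, the analyst cannot correct for it later. If the treatment effect itself changes between 24 and 48 h, the reported difference is an average over an unstated mix of times.

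What is at stake is the precision and interpretability of the only planned post-operative lung-function measure. It is not a primary outcome, nor among the outcomes defined under Secondary outcomes.

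**Working it through.** **The plan's own figures.** The documents give no power, SD or expected difference for IC, so there is no IC figure to reproduce. The only power statements concern pain and opioid use (86% and 98%). With 39 per arm, two-sided alpha 0.025 and a treated-arm SD of 0.7 times the control SD, a normal approximation gives 87.4% and 98.0%. Those figures hold and do not bear on this point.

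**Inputs from the documents.** Slots at 24, 36 and 48 h with windows of ±1, ±2 and ±2 h (Table 2); 39 patients per arm and 5% dropout (Number of subjects), so 39 × 0.95 ≈ 37 evaluable per arm.

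**Step 1: spread of measurement time.**
- Range if the table is followed: 24 − 1 = 23 h to 48 + 2 = 50 h.
- Equal use of the three slots: mean 36 h, SD = √[((−12)² + 0² + 12²)/3] = √96 = 9.8 h.
- Even spread over 23 to 50 h: 27/√12 = 7.8 h.
- All patients in one slot: close to 0. The plan allows any of these.

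**Step 2: chance difference in mean time between arms.** With equal use of the slots, the standard error is 9.8 × √(2/37) = 2.3 h (2.2 h with 39 per arm). The expected difference is 0 when timing does not depend on arm.

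**Step 3: noise added to IC (illustration).** Assume that IC recovers linearly by s SDs per 24 h, where the SD is that of the IC change at a fixed time. The variance is then multiplied by 1 + (s × 9.8/24)² = 1 + s²/6. The reference is a difference detectable with 80% power at two-sided alpha 0.05 and 37 per arm: (1.960 + 0.842) × √(2/37) = 0.65 SD.

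| Assumed s (SD per 24 h) | Variance factor | Effective n (37/factor) | Power, from 80% |
|---|---|---|---|
| 0.25 | 1.01 | 36.6 | 79.6% |
| 0.5 | 1.04 | 35.5 | 78.4% |
| 1.0 | 1.17 | 31.7 | 73.7% |

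In 20,000 simulated trials per setting with the same timing in both arms, the bias was 0 to within 0.001 SD and the type I error was 4.8% to 5.1%.

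**Step 4: what bias would require.** Bias equals s × (difference in mean hours)/24. A hypothetical 6 h difference gives 0.25 × s, or 0.06 to 0.25 SD over the same range of s. Such a difference is 6/2.3 = 2.6 standard errors of the chance difference in step 2, so it would need a systematic cause.

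**The case against.** A reader might infer that the change in IC confounds treatment with time since surgery, because the Background expects better analgesia to allow earlier extubation and mobilisation, and so perhaps earlier testing in the active arm. The documents do not support that as a finding. Allocation is random: "The subjects will be randomized in blocks of 4 to ensure a 1:1 ratio of placebo to treatment groups". Those around the measurement do not know the arm: "The study investigators, surgeon administering the medications, operating room staff and ICU/floor staff will all remain blinded". Timing therefore has the same expected distribution in both arms unless treatment itself shifts it.

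The extubation route is weak on the plan's own rules. Intubation beyond 16 h is a withdrawal criterion, and the first IC slot opens at 23 h, so most patients should have been extubated at least 23 − 16 = 7 h earlier. Alertness and willingness to cooperate could still affect timing, but nothing shows that they do so differently by arm.

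It can also be said that a flexible window protects completeness for an effort-dependent bedside test, and that the loss of power is small unless IC recovers quickly. Both points stand. The first is a reason to keep a fallback reading, not to leave the target unnamed. The second limits how much the point matters. Neither explains why the slot is unstated or why the hour is left out of the analysis.

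**Conclusion.** The point holds as a minor one. A single IC reading falls in an unspecified slot among three, and raw mean change is compared with no account of when it was taken. The main cost is noise: a timing SD of about 9.8 h if the slots are used equally, less if practice settles on one. How much this matters for IC cannot be determined, because the documents give neither an SD nor a recovery rate. The fall from 80% power to between 79.6% and 73.7% rests on assumed linear recovery of 0.25 to 1.0 SD per day, alpha 0.05 and 37 per arm. Bias remains conditional on a timing difference that the documents do not show.

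The footnote read alone might also suggest that IC can be taken at any hour over two days. The Table 2 marks and windows narrow this to about 23 to 50 h. The conclusions on pain and opioid use are unaffected.

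As a side note, the baseline forced vital capacity has no follow-up or stated use. The vital capacity in Appendix IV is an extubation criterion, not a study follow-up value.

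**What to change.** 1. In footnote 3 and under Other variables, name one of the existing Table 2 times, with its window, as the target for the single post-operative IC. A target before the last slot leaves room for a later reading. Mark the other columns as fallback only.
2. Record the actual date and time of the test.
3. If the patient cannot perform the test at the target time, accept and analyse a later reading on POD 1-2. Report off-target and missing values by arm, with reasons.
4. Replace the comparison of mean change with a linear regression of post-operative IC on treatment, pre-operative IC and hours since leaving the OR. If the variances before and after surgery are equal and their correlation is ρ, adjusting for the pre-operative value multiplies the variance of the comparison by (1 + ρ)/2 relative to raw change, which is never above 1. Hours are observed after randomisation, so also show the result without that term.
5. State the purpose of the baseline forced vital capacity, for example as a baseline descriptor, or drop it.

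The cost is protocol wording, one recorded time per patient and slightly tighter ward scheduling, with possibly a few off-target or missing readings. No visit, measurement or patient is added.

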**Appendix II: Pain assessment tools**

**Adult Nonverbal Pain Scale (NVPS)**

**Table 4: Revised Adult Nonverbal Pain Scale**

	0	1	2	Score
1. Face	No particular expression or smile	Occasional grimace, tearing, frown or wrinkled forehead	Frequent grimace, tearing, frown or wrinkled forehead	
2. Activity (movement)	Lying quietly, normal position	Seeking attention through movement of slow cautious movements	Restless activity and/or withdrawal reflexes	
3. Guarding	Lying quietly, no position of hands over areas of body	Splinting areas of body, tense	Rigid, stiff	
4. Physiologic I (vital signs)	Stable vital signs, no change in past 4 hours	Change over past 4 hours in any of the following: SBP > 20 HR > 20 RR > 10	Change over the past 4 hours in any of the following: SBP > 30 HR > 25 RR > 20	
5. Respiratory	Baseline RR/SpO 2 Compliant with ventilator	RR > 10 above baseline or 5%↓ SpO 2 Mild asynchrony with ventilator	RR > 20 above baseline or 10%↓SpO 2 Severe asynchrony with ventilator	
Revised Nonverbal Pain Scale (NVPS)				Total

Abbreviations: HR, heart rate; RR, respiratory rate; SBP, systolic blood pressure; SpO2, oxygen saturation as measured by pulse oximetry.

*Referenced with permission from Strong Memorial Hospital, University of Rochester Medical Center, Rochester, NY.*

**Numeric Rating Scale (NRS)**

When evaluating pain, the care provider is to explain to the patient that "0" represents "no pain" and that "10" represents the "worst possible pain". Patients are to indicate the number that best reflects the intensity of pain that they are currently experiencing. Any score ≥ 4 requires a pain management plan to be implemented.

Scores:        1-3 = mild pain  
                   4-7 = moderate pain  
                   8-10 = severe pain

[figure not shown]
**Appendix III: Brief Pain Inventory (Short Form)**

1. Throughout our lives, most of us have had pain from time to time (such as minor headaches, sprains, and toothaches). Have you had pain other than these everyday kinds of pain during the last week?

Yes

No

2. On the diagram, shade in the areas where you feel pain. Put an X on the area that hurts the most.

3. Please rate your pain by circling the one number that best describes your pain at its *worst* in the last week.

0	1	2	3	4	5	6	7	8	9	10
No										Pain as bad as
Pain										you can imagine

4. Please rate your pain by circling the one number that best describes your pain at its *least* in the last week.

0	1	2	3	4	5	6	7	8	9	10
No										Pain as bad as
Pain										you can imagine

5. Please rate your pain by circling the one number that best describes your pain on the *average*.

0	1	2	3	4	5	6	7	8	9	10
No										Pain as bad as
Pain										you can imagine

6. Please rate your pain by circling the one number that tells how much pain you have *right now*.

0	1	2	3	4	5	6	7	8	9	10
No										Pain as bad as
Pain										you can imagine

7. What treatments or medications are you receiving for your pain?

8. In the last week, how much relief have pain treatments or medications provided? Please circle the one percentage that most shows how much *relief* you have received.

0%	10%	20%	30%	40%	50%	60%	70%	80%	90%	100%
No Relief										Complete Relief

9. Circle the one number that describes how much, during the past week, pain has interfered with your:

A. General Activity

0	1	2	3	4	5	6	7	8	9	10
Does not Interfere										Completely Interferes

B. Mood

0	1	2	3	4	5	6	7	8	9	10
Does not Interfere										Completely Interferes

C. Walking Ability

0	1	2	3	4	5	6	7	8	9	10
Does not Interfere										Completely Interferes

D. Normal Work (includes both work outside the home and housework)

0	1	2	3	4	5	6	7	8	9	10
Does not Interfere										Completely Interferes

E. Relations with other people

0	1	2	3	4	5	6	7	8	9	10
Does not Interfere										Completely Interferes

F. Sleep

0	1	2	3	4	5	6	7	8	9	10
Does not Interfere										Completely Interferes

G. Enjoyment of life

0	1	2	3	4	5	6	7	8	9	10
Does not Interfere										Completely Interferes

Scoring:

Pain Severity Score = Mean of items 3–6 (pain at its worst, pain at its least, average Pain Interference Score = Mean of items 9A–9G (interference of pain with: general activity, mood, walking, normal work, relations, sleep, enjoyment of life)

Copyright 1991 [name]  
 Pain Research Group  
 Reprinted with permission.

**Appendix IV: Criteria for extubation**

URMC, Strong Memorial Hospital, Cardiovascular Intensive Care Unit  
Cardiac Surgery Practice Guideline

Postoperative Cardiac Surgery Weaning From Mechanical Ventilation Guideline

**This guideline is not to be used for the post-operative Ventricular Assist Device or Heart Transplant patient.**

**1. Criteria to initiate the Fast Track Protocol**

- a. Chest tube drainage <100cc/hour
- b. Core temperature  $\geq 36.0^{\circ}$  C
- c. Hemodynamic stability with no escalation of care
  - i. Cardiac Index  $> 2.2$
  - ii. SBP 90-140 with or without inotropes or vasoactive medications
  - iii. Heart Rate <120 bpm
- d. Satisfactory arterial blood gases (ABGs) on full ventilation
  - i. PO2 >70 and PCO2 <45 on 40% FIO2, peep 5-8

[figure not shown]
**2. Extubation Criteria**

- a. Awake without stimulation
- b. Adequate reversal of neuromuscular blockade (able to hold head off pillow for 3 seconds or more)
- c. Acceptable respiratory mechanics
  - i. Tidal Volume >5mL/kg
  - ii. Vital Capacity >10 – 15 mL/kg
  - iii. Spontaneous respiratory rate <24 /min
- d. Acceptable arterial blood gases (ABGs) on 5 cm or less CPAP
  - i. PO2 >70, PCO2 <50 on 40% FIO2, peep 5-8

Guidelines are intended to be flexible. They serve as reference points or recommendations, not rigid criteria. Guidelines should be followed in most cases, but there is an understanding that, depending on the patient, the setting, the circumstances, or other factors, guidelines can and should be tailored to fit individual needs.

*Referenced from Strong Memorial Hospital, University of Rochester Medical Center, Rochester, NY.*

